## **1. Abstract**

The role of the motor cortex in the hemisphere spared by stroke (contralesional motor cortex) in motor performance during post stroke recovery is still unclear. Here we propose to identify the role of contralesional motor cortex in motor performance and post stroke recovery. We will carry out experiments that first identify the extent of stroke and brain areas involved in a motor task using functional MRI of the brain and TMS. We will then determine the functional role of the contralesional motor cortex by studying the effect of low frequency and high frequency repetitive transcranial magnetic stimulation (rTMS) of primary motor cortex (M1) (Chen et al. 1997) on interhemispheric inhibition (IHI) (resting and active) and motor cortex excitability (short interval intracortical excitability and corticospinal excitability) and behavior. We will thereby also identify rTMS protocols that enhance motor performance in stroke patients.

## **2. Introduction and Background:**

It is well known that the motor area of one hemisphere of the brain (motor cortex) controls the movement of the opposite of the body. However, it is not clear whether as

the movement becomes more complicated, the motor cortex of both hemispheres of the brain are involved. Currently the role of the motor cortex on the same side of the body (referred to as ipsilateral motor cortex) in hand performance remains controversial. We demonstrated previously in healthy subjects that transiently lowering the activity of ipsilateral motor cortex improved the performance of the opposite hand. What is not known are the mechanisms involved in these changes of behavior. Transcranial magnetic stimulation (TMS) is a device that allows the non-invasive stimulation of the brain. When brain is stimulated repetitively at a very low rate and low intensity for about 15 minutes, the stimulated brain area becomes less active. This effect lasts 10 minutes and is called a “transient artificial lesion” as it mimicks the effects of transiently interfering with the function of the stimulated brain area. In the present study we will conduct experiments using repetitive TMS to downregulate the activity of the motor area as in previous experiments and measure its effect on activity of motor cortex of both hemispheres. We will study healthy subjects and this collected data will provide normative values for task related changes in M1s and their interactions – a prerequisite to studying abnormalities in stroke patients during motor recovery. It would be important to understand the effects in more detail for the design of treatment strategies in patients after stroke, which will be a topic of future studies.

In most patients with stroke, only one side of the brain is affected by the stroke (affected hemisphere) resulting in weakness of half of the body opposite to the side of the stroke. Over the recent years, researcher discovered that the side of the brain, that is spared by the stroke (non-affected hemisphere) may support the recovery after stroke. However,

there is also a question whether the non- affected hemisphere may interfere with the process of recovery. It is currently not known what factors influence the activity of non- affected hemisphere to either support or interfere with the recovery of stroke. A better understanding of those events is critical to development of optimal therapeutic strategies. For example, non-invasive stimulation of specific areas of the non- affected hemisphere may help to improve functional recovery following stroke. The objectives in this application are to define the factors that influence the activity in the non- affected hemisphere to either support or interfere with the recovery after stroke. We will study the area of the brain that controls movements called motor cortex of the non- affected hemisphere (non- affected motor cortex) as it relates to motor function post-stroke.

In a longitudinal study of stroke patients, non- affected motor cortex reorganization will be assessed in two Specific Aims. In the first Specific Aim, we will determine the extent of functional and structural non- affected motor cortex reorganization using complementary techniques of transcranial magnetic stimulation (TMS), functional and structural MRI of the brain. In the second Specific Aim, the contribution of non- affected motor cortex reorganization to the recovery of motor function will be studied. Repetitive TMS will be used to transiently disrupt non- affected motor cortex function, thereby determine its role for the motor performance of the paretic limb. rTMS related improvement of motor performance would identify a supportive role of contralesional M1 while deterioration of motor performance would indicate its detrimental role. Different rTMS protocols will be applied to non- affected motor cortex to determine

whether non- affected motor cortex can be primed to enhance restorative therapy.

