### 3. Objectives:

**A. Specific Aim #1: *Define key factors that determine the reorganization of contralesional M1 during post stroke recovery process by comparing M1 excitability of stroke patients to that of healthy subjects.*** Our working hypothesis is that the extent of M1 and/or corticospinal tract (CST) damage, as measured by the electromyographic response to TMS of lesioned M1, stroke lesion volume, increased fractional anisotropy (FA) asymmetry of the CST, and quality of wrist/finger extension movements, will determine the extent of contralesional M1 reorganization. In a subset of patients we will also use electroencephalography and TMS to determine the additional key factor of connectivity between the lesioned and the non- lesioned M1 in the post- stroke reorganizational process of contralesional M1.

**B. Specific Aim #2: *Determine the role of contralesional M1 in motor performance during the post stroke recovery process.*** Our working hypothesis is that, during recovery, contralesional M1 contributes to improved motor performance and recovery of the paretic hand in patients with larger M1 and/ or CST damage. Specifically, the extent of M1 and/or CST damage as measured by the electromyographic response to TMS of lesioned M1, lesion volume, increased FA asymmetry of the CST, and quality of wrist/finger extension movements(Nijland et al. 2010) will determine whether contralesional M1 plays a supportive or detrimental role in post-stroke recovery process.

At the completion of this project, we expect to have identified the extent to which

contralesional M1 reorganization determines motor performance during the different phases of post-stroke recovery and can be targeted by interventions depending on its “state” (role) in the recovery process. This latter knowledge would be expected to have a substantial positive impact on treatment for stroke patients as it will provide crucial evidence to develop evidence based TMS treatment protocols that are tailored to the state of therapeutic target. The clinically important question of whether decreasing contralesional M1 activity in patients post stroke is always helpful or at times is detrimental will be addressed.

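### The only stated rule for reading the role of contralesional M1 from the rTMS effect is reversed for a stimulus meant to reduce M1 activity

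*Combined protocol and SAP*

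**What the plan says.** Section 2 (Introduction and Background) introduces the second aim with "Repetitive TMS will be used to transiently disrupt non- affected motor cortex function", so as to learn what that area does for the paretic limb. The next sentence gives the inference rule: "rTMS related improvement of motor performance would identify a supportive role of contralesional M1 while deterioration of motor performance would indicate its detrimental role". The sentence after that begins "Different rTMS protocols will be applied to non- affected motor cortex to determine" and concerns priming for therapy.

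Earlier in section 2, low-rate stimulation for about 15 minutes is described as leaving the stimulated area less active. The effect is likened to a temporary lesion, "as it mimicks the effects of transiently interfering with the function of the stimulated brain area", and the planned experiments are described as "using repetitive TMS to downregulate the activity of the motor area".

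Section 3 (Objectives, Specific Aim #2) gives the working hypothesis that "contralesional M1 contributes to improved motor performance and recovery of the paretic hand in patients with larger M1" or corticospinal tract damage. Its closing paragraph asks "whether decreasing contralesional M1 activity in patients post stroke is always helpful or at times is detrimental".

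In section 4.4, Study #1 applies 1 Hz rTMS at 90% of motor threshold for 15 min, with the stated purpose of reducing contralesional M1 function, and compares it with sham. Study #3 takes the supportive or detrimental role from the effect of this down-regulation and trains a binary classifier on positive or negative responses. Neither study says which response means which role.

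**The concern.** The role of contralesional M1 is the answer that Specific Aim 2 is meant to deliver. The plan infers it indirectly, by turning the area down and watching performance. The conclusion therefore depends on the rule that converts the direction of the performance change into a role, and the one rule given does not fit the sentence before it.

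If an analyst or author follows it, patients whose performance worsens under down-regulation would be recorded as having a detrimental contralesional M1, although the observation points to an area that was helping. A true pattern of support in patients with more damage would be reported as evidence against the hypothesis in section 3. That section also says the role is to inform stimulation protocols tailored to it, so the label has a stated later use.

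**Working it through.** No sample size, power or error rate is at issue, and the plan gives no figure to reproduce. The check is one of sign.

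**Inputs**

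- Direction of the stimulus: M1 activity is lowered (section 2; section 4.4, Study #1 and Study #3).
- Meaning of a supportive role: M1 itself contributes to better performance of the paretic hand (section 3, Specific Aim #2).
- The rule as written: improvement means supportive, deterioration means detrimental (section 2).

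**Sign check.** Let *s* be the effect of M1 activity on paretic-hand performance (positive if supportive, negative if detrimental) and *d* the change in M1 activity produced by rTMS. The expected change in performance has the sign of *s* × *d*. Here *d* is negative.

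| True role of M1 | *s* | *d* | Sign of *s* × *d* | Observed | Rule as written | Labels exchanged |
|---|---|---|---|---|---|---|
| Supportive | + | − | − | Deterioration | Detrimental (wrong) | Supportive (right) |
| Detrimental | − | − | + | Improvement | Supportive (wrong) | Detrimental (right) |

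The written rule is right in 0 of 2 rows and the exchanged rule in 2 of 2.

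**Could the rule be meant for a facilitatory stimulus?** With *d* positive it would be correct, so the question is whether the plan ties the role to such a stimulus.

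- The sentence before the rule specifies disruption.
- Study #1 is described as reducing M1 function, and Study #3 derives the role from that down-regulation.
- Section 8.1 lists 1 Hz and 0.1 Hz as the frequencies used. It describes 0.1 Hz as without effect on excitability, and 0.9 Hz for 15 min, the nearest described to 1 Hz, as lowering it. So 0 of the 2 listed frequencies is described as facilitatory.
- The only other rTMS setting in section 4 is an 80% intensity, in healthy subjects.

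**Could the labels describe the stimulation and not the area?** The rule assigns the role to contralesional M1, and section 3 uses the terms in the same way. The closing question of section 3 rates the act of decreasing M1 activity. On that scale a worse result makes the decrease detrimental, which makes M1 supportive. Section 2 calls M1 itself detrimental for the same observation. The two statements conflict unless the labels in section 2 are exchanged.

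**Would the Study #3 validation reveal the reversal?** No. If both classes are renamed throughout, sensitivity and specificity trade places, as do the positive and negative predictive values, and overall accuracy is unchanged. Cross-validation cannot show that the names are the wrong way round.

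**The case against.** The strongest reply is that this is a wording slip in a background section. Section 6 refers the statistical analysis to the study sections, and none of their models applies the sentence. The mixed models estimate rTMS effects without role labels, and the classifier predicts positive or negative responses. The intended logic can be inferred from the lesion analogy in section 2 and the hypothesis in section 3, and a mislabel could be put right at reporting because the signed effects survive. All of this is fair, and it limits the harm to interpretation. It does not remove the error: Study #3 sets out to predict the role, some translation from response to role is therefore needed, and the only one written down is reversed.

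A second reply is that the Abstract speaks of high-frequency as well as low-frequency rTMS and section 2 mentions different protocols. The Abstract and section 8.1 do differ on the frequencies used and need to be reconciled. That is a reason to say which kind of stimulation the rule covers. It does not rescue a rule that directly follows a sentence about disruption.

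Third, the sign check takes the plan's premise that stimulation lowers M1 activity. Study #1 notes that effects differed by intensity in preliminary data, so the premise need not hold in every subject. This stands as a limit: the check tests the rule against the plan's own premise and says nothing about any individual's physiology.

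The earlier healthy-subject result in section 2, that "transiently lowering the activity of ipsilateral motor cortex improved the performance of the opposite hand", might look like an illustration of the problem. Which hand is meant is unclear, so nothing here rests on it.

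**Conclusion.** The concern holds. Given a stimulus intended to reduce M1 activity, the rule in section 2 assigns the opposite role in both branches, and no other section states the mapping correctly. This must be corrected, because the sentence is the plan's only statement of how the central conclusion of Specific Aim 2 is to be read.

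The size is a complete reversal of direction; no numerical effect is claimed. The conclusion rests on two premises, both from the documents: that rTMS lowers contralesional M1 activity, and that a supportive role means M1 contributes to performance. The reported conclusion would be inverted only if the rule is applied as written, and Study #3 is affected only if its classes are turned into roles by it. The signed rTMS-versus-sham effects, the mixed-model estimates and the section 3 question about decreasing M1 activity are untouched.

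**What to change.** 1. In section 2, exchange the two labels and state the comparison. For example: *Deterioration of paretic-hand performance after down-regulating rTMS, relative to sham, would indicate a supportive role of contralesional M1; improvement relative to sham would indicate a detrimental role.*
2. In section 4.4, Study #3, add a sentence that restates this mapping and says which response class, positive or negative, corresponds to which role.

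The cost is one corrected sentence and one added sentence. Data collection, models and sample size stay as they are.

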### 3. Objectives:

**A. Specific Aim #1: *Define key factors that determine the reorganization of contralesional M1 during post stroke recovery process by comparing M1 excitability of stroke patients to that of healthy subjects.*** Our working hypothesis is that the extent of M1 and/or corticospinal tract (CST) damage, as measured by the electromyographic response to TMS of lesioned M1, stroke lesion volume, increased fractional anisotropy (FA) asymmetry of the CST, and quality of wrist/finger extension movements, will determine the extent of contralesional M1 reorganization. In a subset of patients we will also use electroencephalography and TMS to determine the additional key factor of connectivity between the lesioned and the non- lesioned M1 in the post- stroke reorganizational process of contralesional M1.

**B. Specific Aim #2: *Determine the role of contralesional M1 in motor performance during the post stroke recovery process.*** Our working hypothesis is that, during recovery, contralesional M1 contributes to improved motor performance and recovery of the paretic hand in patients with larger M1 and/ or CST damage. Specifically, the extent of M1 and/or CST damage as measured by the electromyographic response to TMS of lesioned M1, lesion volume, increased FA asymmetry of the CST, and quality of wrist/finger extension movements(Nijland et al. 2010) will determine whether contralesional M1 plays a supportive or detrimental role in post-stroke recovery process.

At the completion of this project, we expect to have identified the extent to which

contralesional M1 reorganization determines motor performance during the different phases of post-stroke recovery and can be targeted by interventions depending on its “state” (role) in the recovery process. This latter knowledge would be expected to have a substantial positive impact on treatment for stroke patients as it will provide crucial evidence to develop evidence based TMS treatment protocols that are tailored to the state of therapeutic target. The clinically important question of whether decreasing contralesional M1 activity in patients post stroke is always helpful or at times is detrimental will be addressed.

#### **4. Study design and Methods:**

The measurements and interventions described will be obtained at 2 time points in all patients (1 and 6 months post stroke). The data will be compared to the results of healthy age matched controls to establish abnormalities

##### **4.1. Studies pertaining to Specific Aim #1: *Define key factors that determine the reorganization of contralesional M1 during post stroke recovery process.***

Motor function assessment post-stroke. In all patients, motor functions will be evaluated in 3 categories of measurements: motor function, motor kinematics and overall function in activity of daily living, to include measures that reflect the behavioral impact of CST integrity. In the first category motor function will be determined using (1) Wolf Motor Function Test (WMFT)(Wolf et al. 2001) and (2) Perdue Pegboard test (Buddenberg and Davis 2000; Mathiowetz et al. 1985) (3) Jebsen Test (Jebsen et al. 1969). Patients may be videotaped during performance of these tests so that scores obtained during testing can be verified. In the second category, laboratory-based measures of upper extremity

movement kinematics will be obtained. In a third category, the use of the paretic arm outside the laboratory will be quantitatively and qualitatively evaluated using the Motor Activity Log MAL (Uswatte et al. 2006). Patients will be contacted by phone 3 – 4 times between the time of stroke until the final study visit in order to complete the MAL. The first phone call will be 5 - 10 weeks after their stroke date. The second call will be 9 – 15 weeks after their stroke date. The third phone call will be 14 – 20 weeks after stroke. The fourth phone call will be 19 – 24 weeks after stroke. In all cases, a randomization process will determine the exact week of contact. A one-week window will be allowed for making contact and completing the MAL.

Stroke date.

Window for first call: 5 weeks – 10 weeks post stroke.

Window for second call: 9 weeks – 15 weeks post stroke.

Window for third call: 14 weeks – 20 weeks post stroke.

Window for fourth call: 19 weeks – 24 weeks post stroke.

Sample script:

Script.

- Hello [name of subject], this is [name of coordinator] calling from [name] lab, how are you?

- Do you have a few minutes to answer some questions about how you're using your hand and arm? This should take about 15 minutes.

- This questionnaire is 30 questions and each question has two parts. I'll name a task and ask you how often you use your affected side to do that task. You'll give me a number on a scale from 0 to 5 where 0 is "not at all" and 5 is "the same as before my stroke". Then I'll ask you how useful your hand is while completing these tasks and you'll give me a number from 0 to 5.

- Do you have any questions?

- In the past week how often have you used your affected hand to \_\_\_\_? And how useful was your hand while doing \_\_\_\_?

- Complete Motor Activity Log with remaining questions.

4.1.1. Structural and functional MRI, data acquisition: All subjects will be scanned. The MRI will be performed on a Siemens 3T Prisma scanner located in the Biomedical Imaging Center (BITC) at Emory University. High resolution T1 weighted images, Flair images and DTI images of the brain will be done to determine the location and size of the stroke and changes in white matter. Arterial spin labeling (ALS) will be used to quantify the blood flow. Functional magnetic imaging of the brain (fMRI) will be used to determine hand movement related activity in M1 of all subjects. For this purpose standard EPI sequences will be obtained. The experiment will run under the control of Presentation® software. Prior to being placed in the scanner, subjects will be given ample time to practice the experimental motor task with both hands at least one day prior to the fMRI experiment.

4.1.2. EMG recording during the motor task in the scanner: The subject's EMG from the extensor carpi ulnaris muscle ECU of both arms will be recorded with MRI compatible shielded surface electrodes, band pass filtered, amplified (MRI compatible amplifier), digitized, sampled at 1-kHz frequency, and stored for offline analysis (LabVIEW, National Instruments, Texas, USA, BrainVision, Brain Products, USA).

4.1.3. MRI data analysis:

*Brain morphometry and CST:* From the T1-weighted image, the cross-sectional area of the left and right cerebral peduncles will be determined (Schaechter et al. 2008). We will measure M1 volume and cortical thickness using FreeSurfer (<https://surfer.nmr.mgh.harvard.edu>). The distance between representations of the white-grey matter boundary and cortical surface will be calculated across each point of the cortex to produce approximations of cortical thickness and then applied to a standard atlas to extract thickness in the pre-specified region of M1 (Desikan et al. 2006; Fischl and Dale 2000). The total lesion volume will be computed using MRIcron software, and corrected for differences in head size by dividing it by the total intracranial volume. The CST in each hemisphere will be reconstructed using TRACULA (TRActs Constrained by UnderLying Anatomy; (Yendiki et al. 2011)) and the DTI processing stream as part of the FreeSurfer image analysis package.

*Functional MRI:* tfMRI and rsfMRI data will be processed using the minimal preprocessing pipeline (Glasser et al. 2013) which includes motion correction, cross-modal registration, and conversion to surface- and volume-based standard space.

Following minimal preprocessing, the task-based fMRI data will be surface-smoothed to 6mm FWHM and entered into a multiple regression analysis with head motion parameters included as regressors of no interest. Temporal derivatives will be added to the model accommodate subject-to-subject variation in hemodynamic response functions. Subjects with right hemisphere lesions will be flipped about the X axis so all lesions are in the same hemisphere. Whole brain and region of interest based analysis will be performed.

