## **5. Participant Selection:**

*Stroke patients:* For SAs # 1-2, subjects will be adult females and males, ages 40-80 years with (1) one cerebral ischemic infarction < 1 month affecting the primary motor output system of the hand at a cortical (M1) level as defined by MRI of the brain, (2) paresis of the hand for more than 3 days after their cerebral infarction ( $MRC \leq 4$ - of wrist- and finger extension/flexion movements), (3) extension of the wrist ( $MRC \geq 3$ , > 10 degree) at the time of the enrollment into the study, (3) no other neurological disorders, (4) no aphasia that prevents subjects from following instructions or their inability to communicate effectively with the study team, (5) no or only mild cognitive impairment but not to the level of dementia (RBANS(Randolph et al. 1998)), (6) no or only mild depression (Hamilton Depression score of <19) (7) no contraindication to TMS or MRI, (8) no intake of CNS active drugs that blocks plasticity (9) the ability to give informed consent. We have chosen this age range because stroke is a disease of elderly people. Only 8.9% of ischemic strokes affect people under the age of 50 years(Fonarow et al. 2010). As plastic changes are likely age-dependent (Sawaki et al. 2003), we would like to exclude “age” as a possible confounding factor by matching our patients post-stroke to the healthy controls (data gathered under R56 NS070879-01) thereby avoiding the possibility that older age may result in a false negative result in our stroke patients.

**Healthy Subjects:** We will study 30 healthy adult females and males, ages 40- 80 years with no neurological or psychiatric diseases and a normal neurological examination, normal MRI of the brain and normal neuropsychological testing(Randolph et al. 1998), no intake of CNS active drugs, no contraindication to TMS and ability to give informed consent.

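### Lesion volume is named as a measure of M1/CST damage but is derived without regard to location; lesion load on M1 and the CST should be added beside it

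*Combined protocol and SAP*

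**What the plan says.** Section 3 (Objectives) sets out the explanatory construct. For Aim 1 it is "the extent of M1 and/or corticospinal tract (CST) damage, as measured by the electromyographic response to TMS of lesioned M1, stroke lesion volume", followed by FA asymmetry of the CST and the quality of wrist/finger extension. Aim 2 relies on the same four measures, lesion volume again among them, to decide whether contralesional M1 is supportive or detrimental. Lesion volume is thus one of four named measures in each aim.

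Section 4.1.3 (MRI data analysis, brain morphometry and CST) gives the derivation: "The total lesion volume will be computed using MRIcron software", and the result is "corrected for differences in head size by dividing it by the total intracranial volume". No other adjustment is stated. The same paragraph plans regional measures: "We will measure M1 volume and cortical thickness using FreeSurfer", the cross-sectional area of each cerebral peduncle, and "The CST in each hemisphere will be reconstructed using TRACULA". Nothing there or elsewhere intersects the lesion with the M1 region or with the tract.

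The mixed models in section 4.3, and those for Study #2 in section 4.4, do not name lesion volume as a covariate. Study #3 in section 4.4 takes its predictors from the variables of Aims 1 and 2.

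**The concern.** The construct concerns a place (the motor output system), while the derived variable concerns only a size. Two patients with equal head size and equal infarct volume receive the same score whether the infarct lies mostly in M1 or mostly outside it. If the sizes differ, the larger always scores as more damaged.

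At stake is the interpretation of Study #3, which looks for the measures that best predict the role of contralesional M1. If the only lesion-based candidate is total volume, coverage of M1 or the CST cannot be selected, because it is not offered. If total volume is selected, the result does not separate motor-system damage from general stroke size. The working hypotheses of both aims, read as statements about M1/CST damage, are then tested less sharply on this one indicator than the planned imaging allows.

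**Working it through.** The documents give no figure on this point to reproduce. The check is a comparison of the texts plus illustrations whose inputs are assumptions.

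**1. What the score depends on.** From 4.1.3, score = total lesion volume / intracranial volume (ICV). No location term appears. At fixed ICV, the order of patients is the order of total volume.

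**2. A worked pair (assumed sizes).** Lesion A is 60 mL, of which 0.5 mL lies in M1. Lesion B is 3 mL, of which 2.5 mL lies in M1. ICV is 1500 mL for both.

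| | Total / ICV (as planned) | M1 overlap / ICV |
|---|---|---|
| A | 60/1500 = 4.00% | 0.5/1500 = 0.033% |
| B | 3/1500 = 0.20% | 2.5/1500 = 0.167% |
| Order | A higher, 60/3 = 20 times | B higher, 2.5/0.5 = 5 times |

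If M1 has the same volume in both patients, the percentage of M1 covered also differs by a factor of 5, whatever that volume is. Head size does not rescue the order. With ICV 1700 mL for A and 1300 mL for B, the planned score still puts A ahead by 20 × 1300/1700 = 15.3 times. In the opposite case (A 1300, B 1700), M1 overlap / ICV still puts B ahead by 5 × 1300/1700 = 3.8 times. The pair shows how the formula behaves. It is not a claim that either patient would be enrolled.

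**3. How often the order would be wrong.** This depends on where lesions lie, which the documents do not say. Simulations used spherical lesions and a spherical M1 target (for example, lesion radius 5–25 or 8–30 mm and target radius 6–10 mm):

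| Assumed placement | Pearson correlation, total volume with fraction of M1 lost | Patient pairs in the wrong order |
|---|---|---|
| Anywhere, provided the lesion touches M1 | 0.17–0.41 | 36–44% |
| Lesion centre within 10–20 mm of the M1 centre | 0.46–0.85 | about 9–22% |

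**4. What such a correlation would mean.** Let ρ be the correlation of total volume with M1/CST load. Under bivariate normality, the share of misordered pairs is arccos(ρ)/π. Suppose also that load correlates 0.5 with some outcome and that total volume relates to the outcome only through load. The correlation seen with total volume is then 0.5ρ. The number needed for 80% power at two-sided 0.05 is N = [(1.960 + 0.842)/atanh(r)]² + 3, rounded up. For load itself (r = 0.5), N = 30.

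| ρ (assumed) | Misordered pairs | r seen with total volume | N with total volume |
|---|---|---|---|
| 0.3 | 40.3% | 0.15 | 347 |
| 0.5 | 33.3% | 0.25 | 124 |
| 0.7 | 25.3% | 0.35 | 62 |
| 0.9 | 14.4% | 0.45 | 37 |

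This single-predictor correlation is not an analysis in the plan. The table only puts a scale on what a given ρ implies.

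**The case against.** The strongest reply is that the plan does not rest on total volume. Three other measures are named. The EMG response to stimulation of lesioned M1 and the FA asymmetry of the CST are specific to the motor output system, and wrist/finger extension reflects its function. Section 4.1.3 adds M1 volume, M1 thickness and peduncle area. All this stands. A reader might infer that total volume is the only structural measure able to show M1 damage, or that it is the predictor in both hypotheses; the documents support neither. What remains is narrower. Section 3 does not list M1 volume, M1 thickness or peduncle area as damage measures, 4.1.3 does not tie them to the lesion, and none of them gives the share of M1 or the CST that is infarcted.

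Second, eligibility limits the spread. Section 5 requires an infarct "affecting the primary motor output system of the hand at a cortical (M1) level as defined by MRI of the brain", and wrist extension must be present "at the time of the enrollment into the study". Loss of the whole hand area may often be incompatible with that, so extreme contrasts should not be presented as pairs of eligible patients. This also stands, but the criteria do not bring location into the score. Among patients who all have some M1 involvement, total volume still counts tissue outside M1 in full.

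Third, a reader might infer a definite loss of power in a planned test. The documents do not support that. No mixed model names lesion volume, the subject-type factor already carries coarse location (cortical or subcortical), and Study #3 uses multivariable classifiers. The low simulated correlations also depend on the touch-only placement rule. Centring lesions nearer M1, arguably closer to the eligibility wording, raises them considerably.

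Finally, total volume / ICV is a coherent measure of stroke severity and may matter in its own right. That argues against removing it, but not against adding lesion load.

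**Conclusion.** The mismatch is in the text and needs no assumption: section 3 uses lesion volume to represent M1/CST damage, and 4.1.3 derives it with no reference to M1 or the CST. It affects one of four named indicators, and mainly Study #3, where only total volume would be offered.

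Its size is unknown. Depending on assumed placement, the correlation with M1 load is about 0.2 to 0.85 and roughly 9% to 44% of patient pairs are misordered. These figures rest on spherical lesions and assumed sizes, so they give a range and not an estimate. The point does not invalidate either aim. It is a cheap improvement that brings the measure into line with the stated hypotheses.

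**What to change.** In 4.1.3, add two derived variables:

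- M1 lesion load = 100 × (volume of M1 inside the lesion mask) / (volume of M1)
- CST lesion load = 100 × (volume of the CST inside the lesion mask) / (volume of the CST)

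Take M1 from the FreeSurfer label and the CST from the TRACULA reconstruction. Where infarction distorts the label or tract on the lesioned side, use the mirrored contralesional label and tract, or a template. State beforehand when that substitution applies, and check each overlap visually without knowledge of the rTMS response.

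Name the two loads in section 3 as the structural measures of M1/CST damage for Aims 1 and 2, and list them in the Study #3 predictor set. Keep total volume / ICV in that set, described as the measure of overall stroke size, so that the two can be told apart.

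The cost is an overlap computation on images and segmentations already planned, with no new scans or patients. The downsides are registration and mirroring error, the time for the visual check, and two more predictors in the classifiers.
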